## MONITORING OF THE DIET WITHIN FINMONICA

Data on diet is collected in three different ways in all three monitoring areas:

- 1) The main questionnaire contains 27 questions concerning dietary habits
  - fat (cooking, milk, fat on bread, fatty meat)
  - sugar (with coffee and tea, drinks, sweets)
  - eggs
  - salt (salting habits, salt taste level, salty food stuffs, advice to reduce salt)
  - alcohol
  - vegetables, fruit and berries
  - meal pattern
  - possible changes during the past year

This questionnaire is sent to all subjects.

- 2) A three-day food consumption record concerning a subsample of about 23 % of the original sample. Persons born on 7-12th day of any month are given both oral and written instructions, the record forms, a model form and a return envelope (instructions, a record form and a model form in appendix I-III).

Food consumption records are started on the following morning after receipt of the forms and kept for three days. The completed records are sent in the return envelope to the National Public Health Institute. There they are checked by a nutritionist and those forms not acceptable are rejected. The records are coded with the help of equivalence tables tailor-made for MONICA in order to convert household measures into grams. These are then processed to get data on food consumption and nutrient intake.

The list of foods and nutrients used in the computer system for processing food intake data are:

### 9 main and 25 subgroups of food:

#### 1 cereals

- rye, wheat, other, legumes and nuts

#### 2 vegetables

- potatoes, roots, other

#### 3 fruits and berries

## 4 fat

- margarine, oil, butter

## 5 milk

- milk, cheese, other

## 6 meat

- pork, beef, sausage, inner organs and blood

## 7 fish

## 8 eggs

## 9 drinks and others

- coffee, tea, alcoholic drinks, soft drinks, sugar, syrup, honey, other

Nutrients

- energy in Kcal and KJ
- proteins, carbohydrates, fats
- vitamins A, retinol, thiamine, riboflavine, niasine, vitamin C
- cholesterol
- fatty acids (7 saturated, 1 monounsaturated, 4 polyunsaturated)
- carbohydrates: starch, saccharose, lactose, other
- alcohol
- 24 minerals (K, Ca, Mg, P, S, Fe, Cu, Mn, Zn, F, Se, Mo, Br, Rb, Al, Si, B, Hg, As, Cd, Co, Cr, Ni, Pb)

- 3) Bread fat inquiry is made in the survey situation. Fresh models of bread slices (dark bread, slices about 30 g each with butter amount of 2.5 g, 5 g, 10 g, 15 g) are on the table. The answers to the following three questions are written on the last page of the general questionnaire:

1. Average bread consumption (slices per day)
2. Quality of fat used on bread
3. Quantity of fat used on bread compared to fresh bread models

The scheme of the collection of nutrition data is as follows

general questionnaire by mail	(home)
fat bread inquiry	(health centre by nurse in survey situation)
checking general questionnaire	(health centre by nurse in survey situation)
oral and written instructions for food consumption records, record forms, model form and return envelope	(health centre by nurse in survey situation)
food record form filled in by the subject	(home)
food record form returned by mail	(NPHI)

## INSTRUCTIONS ON KEEPING FOOD CONSUMPTION RECORDS

You are requested to keep a food consumption record during three consecutive days by using the enclosed forms. Please, write down all foods and beverages consumed during those days starting tomorrow morning.

- Start each day on a new page.
- Fill in the first four boxes by a pencil (time, place, description of food and the amount), and leave the rest of the boxes empty.
- Please, check that your name, the date and day of week are written down on every page.

### Time

Write down in this box the exact time when you are eating or drinking something. It is important that you record the right time even if you eat something very little, e.g.a. a few sweets.

### Place

Write down the place of eating, e.g. home, restaurant, cafeteria at work, friend's house etc.

### Description of food

Write down in this box a clear description of the food or beverage that you have consumed in the place you mentioned and at the time you wrote down.

It is important to mention the quality of the food by using exact descriptions. For example whole milk, low-fat milk, skim milk, low-fat cream, whipping cream, Swiss cheese, cottage cheese, salami, bologna sausage, cream cracker, rye cracker, wheat bread, rye bread, etc. Whenever the product has a brand name, please, write that down.

When you describe a dish, write down the method of food preparation (if it is boiled or fried or grilled) and if you know the type of fat that has been used in the preparation, write that down. For example: meatballs fried in butter.

Also write down whether the food is home-made or it is bought ready-made. If you know that your home-made food differs from the "normal" Finnish food, write down the whole recipe. An example of this follows in the enclosed model form.

Use as many lines as you wish to describe the foods properly.

### Portion sizes

Write down the portion sizes of the foods or beverages already described. Use household measures such as coffee cups, tablespoons, teaspoons, decilitres or grams. If you have a kitchen scale use that for weighing for example fruit, slices of bread, portions of salad etc. whenever possible.

Estimate the portion sizes of different foods as follows:

Beverages: Use glasses, cups, or deciliters. Beer can be measured either in bottles or deciliters, and hard liquor in deciliters. Milk or cream added to coffee or tea should be measured in teaspoons or tablespoons.

Soups: Use deciliters whenever you can or describe the size of the portion as small, medium or big portion.

Sauces: Use tablespoons or deciliters. Note that even the amount of meat sauce such as spaghetti sauce should be estimated this way.

Meat and fish dishes: Estimate the amount of meat or fish by comparing it to an egg or by using centimeters or the palm of your hand.

Salads: If you cannot weigh the portion, use deciliters, cups or tablespoons as measures.

Butter and margarine: Use levelled teaspoons or tablespoons.

Sugar: Use pieces of sugar or levelled teaspoons or tablespoons. Remember to mention also sprinkled sugar on top of porridges etc.

Bread and pastry: Use amounts of slices of bread and describe the size of one slice as small, medium or large and the thickness in centimeters (e.g. medium size slice, 1 cm thick). Describe the pastry as small, medium or large, and if you have a scale, weigh it.

Cold cuts: Write down the number of slices and the size of one slice in centimeters or somehow else. Examples: 3 slices of salami, cut in the butchery very thin, 4 slices of Swiss cheese cut at home with a cheese plane, 4 x 6 centimeters each.

Other foods: Use the information given in the package whenever you eat something that has been wrapped such as a chocolate bar or the like to get the weight of the portion.

IT IS VERY IMPORTANT THAT YOU FILL IN THE FORMS AS CAREFULLY AS POSSIBLE.

THANK YOU FOR YOUR CO-OPERATION!

MONICA-Project: Monitoring of  
cardiovascular diseases and their  
risk factors

FINMONICA  
Part of the international  
MONICA study  
co-ordinated by WHO.  
Co-ordination in Finland:  
National Public Health  
Institute, Helsinki

**ACUTE MYOCARDIAL INFARCTION  
REGISTER**  
(1.1.1982 -)

---

**INSTRUCTIONS HOW TO FILL OUT THE RECORD FORM**

The record form has to be completed for every suspected acute myocardial infarction case if the patient is permanent resident of the monitoring area (question 7) and is aged from 25 to 64 yrs. If the patient has a new heart attack within 4 weeks from the onset of the primary attack it is not registered as a new case. If the patient has a new heart attack after 4 weeks from the onset of the primary attack a new record form is completed. The name and complete address of the patient and his/her next of kin are recorded at the top of the record form. Other questions will be answered by choosing the correct or best-fitting alternative and by recording the number to the right of the questions in the box or by writing it down on the lines reserved for this purpose.

---

**INITIAL INFORMATION (to be completed as soon as possible after the onset of attack)**

Background information

1. Name of patient: \_\_\_\_\_  
address: \_\_\_\_\_  
telephone: \_\_\_\_\_

2. Name of spouse or closest relative or person alive: \_\_\_\_\_  
address: \_\_\_\_\_  
telephone: \_\_\_\_\_

- |   |       |
|---|-------|
| 3. Identification number                                    | 1-5   |
| 4. Personal identification code
(includes date of birth) | 6-15  |
| 5. Age (years) at onset of the attack                       | 16-17 |
| 6. Sex
1 male
2 female                                | 18    |
| 7. Municipality   | 19-20 |

01 Joensuu  
02 Outokumpu  
03 Lieksa  
05 Nurmes  
07 Eno  
08 Ilomantsi  
09 Juuka  
10 Kesälahti  
11 Kiihtelysvaara  
12 Kitee  
13 Kontiolahti

14 Liperi  
15 Polvijärvi  
16 Pyhäselkä  
17 Rääkkylä  
18 Tohmajärvi  
19 Tuupovaara  
20 Valtimo  
21 Värtsilä  
25 Turku  
30 Loimaa  
31 Loimaan kunta

32 Alastaro  
33 Aura  
34 Karinainen  
35 Mellilä  
36 Oripää  
37 Punkalaidun  
38 Pöytyä  
39 Vampula  
40 Yläne  
41 Ypäjä

8. Site of first admission 21-22
- |                                      |                                       |
|--------------------------------------|---------------------------------------|
| 01 North Karelia Central Hospital    | 20 Turku University Central Hospital  |
| 02 Joensuu City Hospital             | 21 Turku City Hospital                |
| 03 Outokumpu, health centre          | 22 Other institution in Turku         |
| 04 Lieksa -"-                        | 30 Loimaa District Hospital           |
| 05 Nurmes                            | 31 Other institution in Loimaa region |
| 06 Eno                               | 90 Hospital elsewhere in Finland      |
| 07 Ilomantsi -"-                     | 91 Treated only at home               |
| 08 Juuka -"-                         | 92 Medically unattended               |
| 09 Kitee -"-                         | (only sudden death cases)             |
| 10 Liperi -"-                        |                                       |
| 11 Tohmajärvi -"-                    |                                       |
| 12 Kontiolahti -"-                   |                                       |
| 13 Other insitution in North Karelia |                                       |
9. Was the patient later transferred to the Central Hospital? 23
- 1 yes
  - 2 no
10. Occupation (at present or before retirement) 24
- 1 agriculture
  - 2 forestry
  - 3 industrial, mining, construction etc.
  - 4 office work, service occupation, student etc.
  - 5 housewife
  - 6 retired
11. Occupational status prior to attack 25
- 1 was occupied during 3 months prior to attack
  - 2 was not occupied but this was due to non-medical reasons
  - 3 unable to work, health insurance payment
  - 4 unable to work, disability payment
  - 5 retired because of age
12. History of AMI 26
- 0 yes, confirmed from the hospital records on the basis of register data\*)
  - 1 yes, confirmed
  - 2 yes, not confirmed
  - 3 no
- \*) identification number of the last definite or possible AMI

13. If yes, year of previous AMI	19	27-28
14. First source of information (leading to registration)		29
1 admitted to hospital ward		
2 admitted to out-patient clinic only		
3 autopsy report		
4 death certificate		
5 laboratory report		
6 health insurance report		
7 other source of information (from family doctor, nursing home etc.)		
15. Current smoking (prior to attack if has been smoking during 3 months prior to attack). Number of cigarettes, cigars and pipefuls per day.		30-31
16. Date of onset of the attack		32-37
17. Status at the first examination		38
1 alive		
2 cardiac arrest		
3 deceased (including unsuccessful resuscitation)		
18. Status after 28 days follow-up		39
1 alive		
2 deceased		
19. Was the patient under systematic cardiac rehabilitation during hospitalization		40
1 yes		
2 no		

Complications since the first examination

20. Cardiac arrest		41
1 yes		
2 no		
21. If resuscitated, was the resuscitation successful (the patient was alive at least 24 hours since the resuscitation)		42
1 yes		
2 no		
3 no resuscitation		

## REGISTER DIAGNOSIS (to be completed by the monitoring centre)

22. History of pain (symptoms)	43
1 typical	
2 atypical	
3 other	
4 none	
5 insufficient data	
9 no data	
23. ECG findings	44
1 definite	
2 probable	
3 ischaemic	
4 other	
5 uncodable	
9 no data	
By which criteria of the protocol coded	45
Localization (separate coding instructions)	46
24. Serum enzymes	47
1 abnormal	
2 equivocal	
3 nonspecific	
4 normal	
5 incomplete	
9 no data	
25. Necropsy findings	48
1 definite	
2 possible	
3 negative	
4 no autopsy	
9 insufficient data	
26. Diagnostic category	49
1 definite	
2 possible	
3 primary ischaemic cardiac arrest (if not 1 or 2)	
4 none	
9 insufficient data (only fatal cases)	

Clinical diagnosis

27. Main diagnosis (ICD-code) according to hospital record or death certificate	50-54
Other diagnoses	55-59
	60-64

Laboratory results (if available)

28. Weight (kg)	65-67
29. Height (cm)	68-70
30. S-cholesterol (mmol/l, first value)	71-73
S-HDL-cholesterol (mmol/l, first value)	74-75
31. S-CK (U/l, highest value)	76-79
MB (% , highest value)	80-81
S-GOT (U/l, highest value)	82-85
MB (U/l, highest value)	86-89
total LD (U/l, highest value)	90-93
LD1 (U/l, highest value)	94-97
LD1 (% , highest value)	98-99

FATAL CASES ONLY (TO BE COMPLETED IF PATIENT DIED DURING 28 DAYS SINCE FIRST ONSET OF ATTACK)

32. Date of death (day, month, year)	100-105
33. Survival time	106
1 0-59 minutes	
2 1-23 hours	
3 24 hours or more	
4 apparently less than 24 hours	
5 apparently 24 hours or more	
9 no information	

34. Was autopsy performed 107
- 1 yes, medico- pathological
  - 2 yes, forensic
  - 3 no
35. History of prior CHD
- 1 definite or possible AMI
  - 2 confirmed CHD
  - 3 possible CHD
  - 4 obviously no history of CHD
  - 5 no information
36. ECG: Number of ECGs after the onset of attack  
(to reach the diagnosis) 108  
(if  $\geq 5$ , code 5)
37. Death after an followed invasive procedure (3 days) 109
- 1 yes
  - 2 no
  - 9 no information

Diagnostic data

39. History and medication of CHD  
(only fatal cases)

---

---

---

---

40. Description of present pain symptoms  
(see text next page)

1 localisation \_\_\_\_\_

---

---

---

---

---

2 duration \_\_\_\_\_

---

---

---

---

---

3 impact of nitrates \_\_\_\_\_

---

---

---

---

---

4 intensity and use of analgesics \_\_\_\_\_

---

---

---

---

---

41. Diagnostic laboratory results with dates

date	CK	CK-MB %-U/l	GOT	LD	LD1 %-U/l
------	----	----------------	-----	----	--------------

42. ECG (see text next page)

## INSTRUCTIONS

The record form is completed for every heart attack among persons under 65 years of age when acute myocardial infarction is suspected on the basis of chest pain, ECG or elevated serum enzymes.

If a person dies not medically attended a suspicion of acute myocardial infarction can arise on the basis of typical or atypical symptoms, autopsy findings or previous coronary heart disease.

If a new heart attack occurs within 28 days from onset of a former registered acute myocardial infarction it is considered as a complication of the first one and not registered as a new attack. If a new heart attack occurs later than 28 days from onset of a former registered attack, it must be registered as a new case.

The symptoms of acute myocardial infarction are to be coded as typical when there is a retrosternal pain at the beginning of the attack

- lasting more than 20 minutes
- no definite non-cardiac cause found.

The symptoms are to be coded as atypical when there is atypical pain, shock, vertigo, collapse or acute left ventricular failure in the absence of cardiac disease other than ischaemic heart disease and no definite non-cardiac cause is found.

Serum specimens for cardiac enzyme tests should be drawn at least on the first and second day of treatment. The results have to be recorded in the respective space of the record form.

In addition to the completed record form of every registered case

- pieces of most typical ECGs consisting of at least 3 QRS complexes of all 12 leads and which are taken at least the first, second, third and fifth on days since the onset of attack, and
- a photo-copy of the summary of the hospital record should be sent to the monitoring centre

From the North Karelia Central Hospital, from Turku monitoring centre, from Loimaa District Hospital and from Kuopio monitoring centre the completed record forms will be sent to

AMI REGISTER  
National Public Health Institute  
[name]  
[name]  
([contact])

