### 3. Diagnostic criteria

To enable the diagnostic classification of the cases, information is carefully, and in a standardized way collected on the following diagnostic criteria: symptoms, ECG findings, serum enzymes and necropsy findings (fatal cases). For fatal cases information is collected on the possible history of CHD, too.

The register nurse interviews the patient on pain and other symptoms: If this is not possible the respective information is obtained from patient files. It should be not that case finding can initially be due to other reasons than pain.

The ECG is recorded from all suspect cases on their arrival and during first, second and third days of hospitalization as well as before discharge. During the recording the paper speed should be 50 mm per second. All ECG readings or their copies are submitted to the local monitoring centre for diagnostic classification. The classification and the protocol criteria on which the classification is based are recorded on the record form. The localisation of the myocardial infarction is also coded according to the following instructions

- 1) anterior (V1 - V5)
- 2) lateral (I, aVL, V6)
- 3) inferior (II, III, aVF)
- 4) 1 + 2
- 5) 2 + 3
- 6) other combination

The enzyme pattern is analyzed primarily serum CK ( creatine kinase) enzyme and its MB fraction or LD (lactic dehydrogenase) with its isoenzymes, or SGOT (aspartate aminotransferase) come into question.

To be able to fully evaluate the enzyme results the onset of pain should be determined as exactly as possible. Each enzyme has its own typical pattern in AMI; the schedule for blood sampling should be determined accordingly.

Every monitoring centre is using enzyme determinations according to the local circumstances. The blood sampling schedule and the reference values used are presented below: the MONICA protocol is followed.

It is recommended that the autopsy rate should be as high as possible for fatal cases with suspected CHD and that special attention should be paid to the coronary vessels at the autopsy. The necropsy findings are made available for the monitoring centre to enable the diagnostic classification. The criteria proposed by the MONICA protocol are presented below.

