1.2 Atypical

(i) one or more of the following

- atypical pain
- acute left ventricular failure
- shock
- syncope

AND

(ii) the absence of cardiac disease other than ischaemic heart disease

AND

(iii) no definite non-cardiac cause.

**Note:** The pain should be recorded as atypical if it is of short duration, intermittent with each bout lasting for less than 20 minutes, or appearing at an unusual site (upper abdomen, arms, jaw, neck). Fatal collapse should not be considered as syncope, otherwise all sudden deaths would be coded in this way. Syncope should be reversible. Typical chest pain leading to syncope should not be coded as an atypical symptom.

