### 1.5 Inadequately described

Cases otherwise satisfying criteria for Typical pain but in which the duration of the pain is not described to enable the classification of the symptom as Typical or Atypical.

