### 1.9 Not known

No information on whether symptoms were present.

For diagnostic classification purposes, code 2 is equivalent to code 5; and codes 3, 4 and 9 are equivalent to each other (see the record form).

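### The AMI record form and the register manual give conflicting rules for coding symptoms and supplying ECGs, so the same event can be classified differently depending on which text is followed

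*Protocol*

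**What the plan says.** The coding rules appear twice: in Part III, AMI register, section 3 (the manual), and in the annexed AMI register record form (item 22 and the INSTRUCTIONS page).

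- **Atypical symptoms.** Form: "The symptoms are to be coded as atypical when there is atypical pain, shock, vertigo, collapse or acute left ventricular failure". Manual 1.2 lists atypical pain, acute left ventricular failure, shock and syncope. It adds "Syncope should be reversible" and "Fatal collapse should not be considered as syncope, otherwise all sudden deaths would be coded in this way".
- **Typical symptoms.** The form wants retrosternal pain of more than 20 minutes with no definite non-cardiac cause. Manual 1.1 asks for chest pain with the same duration and exclusion, and its note keeps any further characteristic out of the definition.
- **Symptom code 5.** Form item 22: "5 insufficient data". Manual 1.5: "Cases otherwise satisfying criteria for Typical pain but in which the duration of the pain is not described". Under manual 1.9, for classification "code 2 is equivalent to code 5", while codes 3, 4 and 9 form a second group.
- **ECGs.** The form asks for "pieces of most typical ECGs consisting of at least 3 QRS complexes of all 12 leads", taken at least on days 1, 2, 3 and 5 from onset. Manual section 3: "All ECG readings or their copies are submitted to the local monitoring centre for diagnostic classification". Manual section (2) then has up to four coded: the first, the next two on different dates, and the last on file. Local discretion is allowed only in named situations.

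**The concern.** The symptom code feeds directly into the diagnostic categories of manual section 4. In a death with no other cause found, typical, atypical or inadequately described symptoms are enough for category 2(b)(i). In living patients, categories 1(c) and 2(a) require typical symptoms. A different definition of a symptom code can therefore change whether an attack counts.

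Case fatality is the outcome of the second main null hypothesis, and attack rates enter the first. General Protocol 4.1 relies on recording practice staying unchanged, and 5.2 promises the same methods throughout. Coding is done by a separate register doctor in each of four places (Joensuu, Kuopio, Turku, Loimaa). Two conflicting texts leave room for centres to diverge, or for one centre to drift from one text to the other.

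**Working it through.** The plan states no figure on this point, so the check traces cases through manual section 4 under each text.

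**Fatal cases** (no definite ECG)

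| Case | Manual | Form, read literally |
|---|---|---|
| Collapse with no earlier symptoms; no autopsy, ischaemic history or other diagnosis | code 4, category 5 | code 2, category 2(b)(i) |
| Partial symptom information meeting none of manual 1.1, 1.2 or 1.5; otherwise as above | code 3 or 9, category 5 | if entered as code 5, category 2(b)(i) |
| Symptoms wholly unknown; otherwise as above | code 9, category 5 | code 9, category 5 |
| Ischaemic history or chronic coronary lesion at necropsy, no other cause of death | category 2 | category 2 |
| Recent infarct or recent occlusion at necropsy | category 1 | category 1 |
| Another diagnosis established, not category 1 | category 4 | category 4 |

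Only the first two rows change.

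**Living patients: chest pain over 20 minutes, not retrosternal, no non-cardiac cause.** The manual gives code 1; the form, read literally, gives code 2.

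- Ischaemic, uncodable or absent ECG with abnormal enzymes: the manual gives 1(c). Under the form, 1(b) fails because the ECG is not probable, and 1(c) and 2(a) fail because symptoms are not typical.
- Category 1 not met and no other diagnosis: the manual gives 2(a); the form gives neither 1 nor 2.
- Definite ECG, or probable ECG with abnormal enzymes: category 1 under both.

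The manual itself treats pain in the upper abdomen, arms, jaw or neck as atypical, so this difference concerns only pain in the chest that is not retrosternal.

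**ECGs.** Manual section 3 includes a tracing before discharge, and section (2) requires the last one on file. The form guarantees days 1, 2, 3 and 5 only. If the last tracing is later than day 5, a centre following the form need not send it, and the coder cannot then apply the manual's selection.

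**Direction.** Let N be definite plus possible attacks, D the fatal ones among them, k the deaths added by the form and m the living patients lost. Case fatality moves from D/N to (D + k)/(N + k − m). With D below N, either k or m alone raises it. Two limits apply:

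- This assumes the rate uses categories 1 and 2 only. The protocol does not state which categories enter.
- The form's vertigo rule, and a loosely used code 5, can admit living patients through 1(b), which adds to N alone and lowers the rate. The net sign is not fixed.

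**Size.** k and m are not available. Part IV Table 11 gives 2330 registered events in 1983 without categories. Table 13 estimates definite and possible cases in men but leaves out those found dead without intervention, a group in which affected deaths are likely to fall.

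**The case against.** The strongest reply is that the manual governs. Item 22 is completed at the monitoring centre by the register doctor, manual section 3 says its criteria are the ones used in Finland, and section 4 demands strict application. The form offers code 4 for no symptoms, which the manual illustrates with sudden death. Collapse on the form stands where the manual has syncope and may be a loose paraphrase. The form fixes ECG days, and its reference to typical ECGs may describe the strips cut from each tracing. No text shows a centre coding from the form. A constant error would mainly shift levels, whereas the hypotheses concern trends.

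Much of this stands, and it makes the consequence conditional. It does not remove the conflict:

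- Section 4's demand for strictness concerns the category definitions, not the symptom codes.
- Form items 40 (symptoms) and 42 (ECG) send the user to the conflicting page.
- Manual section 5 refers to the record form for the diagnostic material to be sent, so the ECG pieces are chosen before the register doctor sees anything.
- On the same form, insufficient data is code 9 in items 25 and 26 but code 5 in item 22, which invites error.
- A constant rule need not have a constant effect. The exposed deaths are those without autopsy, so their number would change if the autopsy rate changed.

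A reader might infer that deaths with no symptom information at all become possible coronary deaths. They do not: both texts keep code 9, which the manual groups with codes 3 and 4. A reader might also infer that the ECG instruction pushes cases towards the definite category. The conflict over which tracings are sent is real, but nothing in the protocol shows a direction.

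**Conclusion.** The form and the manual contradict each other on four points: collapse and vertigo, retrosternal pain, the meaning of code 5, and which ECGs are supplied. Where the form is followed, a narrow group of deaths moves from category 5 to category 2: a fatal collapse, or partial symptom information entered as code 5, with no autopsy, no ischaemic history, no other diagnosis and no definite ECG. Some living patients with prolonged non-retrosternal chest pain leave categories 1(c) and 2(a), and the coder may lack tracings that the manual requires.

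The size cannot be stated. A percentage change in case fatality would need the category 5 count, the share of it affected and the categories entering the rate, and the protocol gives none of these. The conclusion rests on the wording alone and on the possibility that some centre, at some time, codes or sends material by the form. If every centre followed the manual throughout, there would be no effect. If practice differed between centres or over time, comparisons of event rates and case fatality would be affected.

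**What to change.** 1. On the form's INSTRUCTIONS page, replace the definitions of typical and atypical symptoms with a reference to manual 1.1 to 1.9.
2. Relabel item 22 code 5 as inadequately described (otherwise typical pain, duration unknown). Code 9 stays as it is.
3. Request copies of all ECGs, with selection for coding as in manual section (2).
4. Limit any re-check of stored records to fatal cases with symptom code 2 or 5, no autopsy and no history of ischaemic heart disease. Fatal cases with such a history and no other cause of death are category 2 in any event.

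The cost is one reprinted form page and a small re-check by the existing register doctors.
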